4.1 Inclusion Criteria

Inclusion Criteria (RA cohort):

- Receiving MTX at stable doses of 10 to 25 mg weekly for at least 12 weeks
- Have a DAS28 of 3.2 or higher (The level of disease activity is considered to be low if the DAS28 is 3.2 or less) (Prevo et al., 1995)
- Written informed consent prior to any study specific procedures
- Over 18 years of age at time of enrollment.

Inclusion Criteria (OA cohort):

- Age- and Sex- Matched to RA cohort. Subjects will not be selected based on grade of OA.
- Diagnosis of osteoarthritis made by physician.

4.2 Exclusion Criteria

Exclusion Criteria (RA cohort):

- History of sensitivity to study medications or any of their excipients
- Previous intolerance to MTX
- Current treatment with antiplatelet therapy
- Absolute indication for anti-platelet therapy
- Need for chronic oral anticoagulant therapy
- Severe hepatic impairment (eg, ascites and/or clinical signs of coagulopathy)
- Renal failure (eGFR <30 or requiring dialysis) by history
- A known bleeding diathesis, hemostatic or coagulation disorder, or prior major bleeding
- Prior stroke
- Active pathological bleeding
- History of intracranial haemorrhage

CONFIDENTIAL

- Life expectancy <12 months based on investigator's judgement
- Patients considered to be at risk of bradycardic events (e.g., known sick sinus syndrome or second or third degree atrioventricular [AV] block) unless already treated with a permanent pacemaker
- Anemia (hematocrit < 27%) by history
- Platelet count < 100,000/ml by history
- Concomitant use of strong CYP 3A inhibitors or inducers
- History of thrombocytopenia or neutropenia
- Pregnant or nursing women, or females with a positive urine and/or serum pregnancy test at screening/baseline
- Females of child bearing potential not using acceptable method of birth control prior to or during study
- Concern for inability of the patient to comply with study procedures and/or follow-up (eg, alcohol or drug abuse)

Exclusion Criteria (OA cohort):

- History of sensitivity to study medications or any of their excipients
- Current treatment with antiplatelet therapy
- Absolute indication for anti-platelet therapy
- Need for chronic oral anticoagulant therapy
- Severe hepatic impairment (eg, ascites and/or clinical signs of coagulopathy)
- Renal failure (eGFR <30 or requiring dialysis) by history
- A known bleeding diathesis, hemostatic or coagulation disorder, or prior major bleeding
- Prior stroke
- Active pathological bleeding
- History of intracranial haemorrhage
- Life expectancy <12 months based on investigator's judgement
- Anemia (hematocrit < 27%) by history
- Platelet count < 100,000/ml by history
- History of thrombocytopenia or neutropenia
- Pregnant or nursing women, or females with a positive urine and/or serum pregnancy test at screening/baseline
- Females of child bearing potential not using acceptable method of birth control prior to or during study
- Concern for inability of the patient to comply with study procedures and/or follow-up (eg, alcohol or drug abuse)

4.3 Subject Recruitment and Screening

Recruitment of patients will come mainly through routine clinical care visits by rheumatologists in the faculty practice at the Center for Musculoskeletal Care. NYU is home to the Center for Musculoskeletal Care and has a special emphasis on Arthritis and Autoimmunity. Over 20,000 rheumatology visits a year are captured at NYU Hospital for Joint Diseases. Approximately 70 new patients are seen each week in rheumatology clinics and practices which can provide 4 to 5 new RA patients a week. Subjects will be recruited by study physicians. Recruitment of patients will come mainly through routine clinical care visits by rheumatologists in the faculty practice at the Center for Musculoskeletal Care and other rheumatology clinics. Physicians at clinical sites will be aware of the current protocol and will be encouraged to speak with their patients. If there is a need for additional patient materials, a separate advertisement will be placed with prior IRB approval. Letters to affiliate physicians may also be written that also would be submitted for IRB approval. Management of DataCore will also be mining the database for our specific recruitment needs.

Target patient population

The target study population is male and female participants over the age of 18 who meet the 1987 American College of Rheumatology (ACR) classification criteria for RA (Arnett et al., 1988) or OA (Altman et al., 1991; Altman et al., 1990; Altman et al., 1986) fulfilling all of the inclusion and none of the exclusion criteria. This study aims to have 25 subjects in the RA cohort complete all study activities, and 10 subjects with OA to

CONFIDENTIAL

match with the RA cohort. To achieve 35 subjects completing the entirety of the study, there will be a maximum total accrual of 60.

4.4 Informed Consent

Investigators must ensure that subjects are clearly and fully informed about the purpose, potential risks, and other critical issues regarding clinical studies in which they volunteer to participate. Freely given written informed consent must be obtained from every subject before clinical study participation, including informed consent for any screening procedures conducted to establish subject eligibility for the study. Written informed consent will be obtained by the research staff member designated by the PI. All written informed consent originals will be maintained for study purposes and review if needed.

4.5 Early Withdrawal of Subjects

4.5.1 Patient Withdrawal

Patients may withdraw from the study at any time and for any reason. Reason for study withdrawal will be documented and may include the following reasons:

- Patient choice;
- At the discretion of the Investigator;
- Development of a contraindication to ticagrelor or MTX;
- Development of a bleeding diathesis, hemostatic or coagulation disorder, or major bleeding;
- Pregnancy;
- Death.

4.5.2 Early Withdrawal Procedures

Patients who withdraw due to an AE or SAE require additional follow-up.

- If a patient is early terminated from the study due to an AE, he/she will be followed until resolution of the event or for 30 days after discontinuation of study medication (whichever occurs first).
- For SAE follow-up, please refer to Section 8.

Patients who are discontinued from study medication for any reason other than an SAE will be encouraged to remain on the study (not be officially withdrawn from the study) and complete all study visits.

5 Study Drug

5.1 Administration of Study Drug

Patients will self-administer study medication twice daily, orally for 30 days.

5.2 Subject Compliance Monitoring

Patients will be trained on study medication dosing prior to beginning treatment. Compliance will be discussed over the phone as needed and during the post dose visit (Day 30).

5.3 Concomitant Medications

Concomitant medications will be reviewed at all study visits.

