1.5 Research Risks & Benefits

1.5.1 Risk of Study Drug

Ticagrelor can cause bleeding that can be serious and sometimes lead to death. Instances of serious bleeding, including internal bleeding, may require blood transfusions or surgery. Subjects taking ticagrelor may bruise and bleed more easily and be more likely to have nosebleeds. Bleeding will also take longer than usual to stop. Subjects who experience any of these symptoms will be informed to call their study doctor immediately and call 911 in the event of an emergency.

Patients who are taking ticagrelor are also at a greater risk of dyspnea. If ticagrelor must be temporarily discontinued (e.g., to treat bleeding or for significant surgery) it should be restarted as soon as possible. Because the primary route of ticagrelor elimination is hepatic metabolism, patients with severe hepatic impairment should not use ticagrelor.

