5.4.2 Return or Destruction of Study Drug

At the completion of the study, there will be a final reconciliation of drug shipped, drug consumed, and drug remaining. This reconciliation will be logged on the drug reconciliation form, signed and dated. Any discrepancies noted will be investigated, resolved, and documented prior to return or destruction of unused study drug. Drug destroyed on site will be documented in the study files.

6 Study Procedures

Study participation includes a 30-day treatment period. Screening and baseline visits may be done on the same day if the subject is able to give fasting blood and does not meet any exclusion criteria.

Table 1: Schedule of Assessments.

	Screening	Baseline	1 and 2 Week Phone call	Day 30
Visit #	1	1 or 2		2 or 3
Day#	- 30 - 3	0		30 ± 5
Informed consent	X			
Medical history	X	X		
Medications	X	X		X
Vital signs/physical exam		X		X
DAS28/CDAI/RAPID3/MDHAQ	X	X		X
ACR responses		X		X
Blood (fasting) collection		X		X
Urine and/or serum pregnancy test for WOCBP only	X	X		
Platelet Activity		X		X
Brachial Artery Reactivity Testing (fasting)		X		X
Dispense study drug		X		
Adverse events	X	X	X	X
Medication compliance/diary			X	X

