6.3 Visit 2 or 3 (Day 30 +/-5): RA cohort only

- Review of medications will be performed;
- Vitals will be recorded and the patient will have a physical exam;
- DAS28, CDAI, RAPID3 and MDHAQ will be performed and recorded;
- ACR responses will be measured;
- Fasting blood will be collected;
- For each subject, no more than 75 cc of blood will be collected in red (no anticoagulant) top, Pax gene tube for genomics, lavender (EDTA anticoagulant) top, green (heparin) and blue (sodium citrate anticoagulant) top tubes. Approximately 40 cc of blood will be used for the different measurements of platelet function, inflammation, immune activation, and other markers of cardiovascular risk, and approximately 30 cc of blood will be used to purify cells, RNA and DNA and then stored in -80C/liquid nitrogen for genetic and functional profiling. The results of the genetic testing will not be shared with the subjects.
- Fasting brachial artery reactivity testing including one time dose of 0.4 mg of nitroglycerin given sublingual. To minimize risk of hypotension, nitroglycerin will not be administered if resting systolic blood pressure is <100 mmHg;
- Adverse events will be reviewed and recorded;
- Medication compliance will be reviewed with the subject.

7 Sample storage for future research

The samples will be stored in the PI's lab without any identifying information other than a code number. The code number will not be based on any information that could be used to identify the subject (for example, social security number, initials, birth date, etc). The master list linking names to code numbers will be kept in a locked file cabinet, separate from all research information. All specimen handling, collection, processing, and storage, will be performed as per regulations and Tisch Laboratory and NYU policy. Specimens will be

CONFIDENTIAL

collected at CMC and transferred to Tisch Laboratory for analysis. Samples will be stored for 10 years after the end of the study, if subjects give permission in their consent form.

7.1 **Optional permission to store samples for future use**

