9.2 Recording of Adverse Events

At each contact with the subject, the investigator must seek information on adverse events by specific questioning and, as appropriate, by examination. Information on all adverse events should be recorded immediately in the source document, and also in the appropriate adverse event module of the case report form (CRF). All clearly related signs, symptoms, and abnormal diagnostic procedures results should be recorded in the source document, though should be grouped under one diagnosis.

All adverse events occurring during the study period must be recorded. The clinical course of each event should be followed until resolution, stabilization, or until it has been determined that the study treatment or participation is not the cause. Serious adverse events that are still ongoing at the end of the study period must be followed up to determine the final outcome. Any serious adverse event that occurs after the study period and is considered to be possibly related to the study treatment or study participation should be recorded and reported immediately.

CONFIDENTIAL

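### After Day 0 the next scheduled question about newly started drugs comes at Day 30 ±5, when dosing is over or nearly over; asking it at the Week 1 and 2 calls is a cheap, low-priority safety improvement

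*Combined protocol and SAP*

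**What the plan says.** Section 5.3 is a single sentence: "Concomitant medications will be reviewed at all study visits". In Table 1 (Section 6) the Medications row is marked at Screening, Baseline and Day 30. The column headed "1 and 2 Week Phone call" carries no visit number, and only two rows are marked in it: adverse events, and medication compliance/diary. Sections 6.1 to 6.3 put the medication review at the same three points; for the Day 30 visit the wording is "Review of medications will be performed".

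Section 4.2 keeps out of the RA cohort anyone on antiplatelet therapy, and also lists "Need for chronic oral anticoagulant therapy" and "Concomitant use of strong CYP 3A inhibitors or inducers". These are entry criteria. No section says what happens if such a drug is started during treatment, although Section 4.5.1 allows withdrawal when a contraindication to ticagrelor arises or at the investigator's discretion.

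Two safeguards act between the visits. Section 9.2 states: "At each contact with the subject, the investigator must seek information on adverse events by specific questioning". Section 1.5.1 says that subjects with bleeding or bruising symptoms "will be informed to call their study doctor immediately and call 911 in the event of an emergency".

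**The concern.** Section 1.5.1 warns that bleeding on ticagrelor can be serious and occasionally fatal. Antiplatelet drugs and anticoagulants are barred at RA entry, but a subject who starts one on Day 3 may not be asked about it until treatment has ended. At that point the review documents the exposure and can do little to shorten it. The withdrawal provision in Section 4.5.1 can act during dosing only if someone learns of the drug during dosing.

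The adverse-event questions find a new drug only if the subject mentions the illness behind it. A drug begun for prevention or for a long-standing condition may not come up. The advice to call the study doctor takes effect once symptoms have appeared. Two staff contacts already fall inside the treatment period, and neither is scheduled to include the direct question.

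The point concerns the RA cohort only. OA subjects receive no study drug and have one visit.

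**Working it through.** The plan states no figure on this point, so there is nothing to reproduce. The check is a reading of the schedule plus a count of days.

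**Inputs**
- Dosing: 30 days (Section 5.1), dispensed once, at Baseline (Table 1). I take Day 0 as the start and Day 30 as the end.
- Next medication review: Day 30 ±5, so Day 25 to Day 35 (Section 6.3).
- Calls: Weeks 1 and 2. Table 1 gives no day; Days 7 and 14 are assumed.
- Numbers: 25 RA completers, 10 OA subjects, accrual cap 60 (Section 4.3).

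**Schedule, row by row**

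| Item | Baseline | Week 1 and 2 calls | Day 30 ±5 |
|---|---|---|---|
| Medications | marked | blank | marked |
| Adverse events | marked | marked | marked |
| Compliance/diary | blank | marked | marked |

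The content of the diary is not described. Section 5.2 treats compliance as a matter of study-drug dosing, and Table 1 keeps Medications as a separate row. The diary therefore cannot be counted as a check for other drugs, though it might pick some up.

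**Dosing time without a direct check, as planned**
- On-drug days from Baseline to the review = min(visit day, 30): min(25, 30) = 25; min(35, 30) = 30. Range 25 to 30 days.
- Dosing days left at that review = max(30 − visit day, 0): 30 − 25 = 5, falling to 0. Range 0 to 5 days.

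**With the question added at both calls**
- Gaps: 7 days, then 14 − 7 = 7 days, then min(visit day, 30) − 14, which is 25 − 14 = 11 to 30 − 14 = 16 days.
- Longest gap: 11 to 16 days.
- Share of on-drug time up to the review that falls after the Week 2 call: 11/25 = 44% to 16/30 = 53%.
- Dosing days left when a drug is found at a call: 30 − 7 = 23, or 30 − 14 = 16.

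In calendar time, without stopping the count at the end of dosing, the gap is 25 to 35 days now, and the longest gap would be 11 to 21 days (35 − 14 = 21).

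**Burden**
- Completer target: 2 × 25 = 50 questions.
- Upper bound, if all accrual beyond the 10 OA subjects is RA: 60 − 10 = 50 subjects, and 2 × 50 = 100 questions.
- At an assumed 1 to 2 minutes each: 50 × 1 = 50 to 100 × 2 = 200 minutes over the whole study.

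Sample size, power and alpha are unaffected.

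**The case against.** The strongest reply is that the plan is coherent and mostly covers the risk already. Review at every visit is a reasonable schedule for a 30-day study. A new anticoagulant or antiplatelet drug would usually follow a clinical event, and a strong CYP 3A inhibitor an intercurrent illness. Section 9.1 counts intercurrent illness as an adverse event, and adverse events are sought at both calls. Section 4.2 has already screened out subjects with a foreseeable need for antiplatelet or anticoagulant drugs. Section 4.3 says physicians at the clinical sites will know the protocol, though that does not reach outside prescribers. The consent pages, which are not available here, may tell subjects to avoid or report other drugs.

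Much of this stands, and it is why the point is low priority. What remains is the subject who starts such a drug and does not mention the reason for it.

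Four stronger readings are tempting and should be resisted:
- A reader might infer that Section 5.3 and Table 1 conflict. They do not, because the calls carry no visit number.
- A reader might take the statement that "the primary route of ticagrelor elimination is hepatic metabolism" as a drug-interaction argument. In Section 1.5.1 it explains why patients with severe hepatic impairment should not use the drug.
- A reader might extend the bleeding rationale to CYP 3A inducers. The documents give no basis for that. Even for strong inhibitors the bleeding purpose is an inference, since Section 4.2 lists the exclusion without a reason.
- A reader might infer bias in the DAS28 or platelet results. Nothing in the documents shows it.

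**Conclusion.** The point holds as a low-priority design improvement. The plan schedules no direct question about newly started drugs between Day 0 and Day 30 ±5, and the one that follows comes with at most five dosing days left. Using calls that are already scheduled would cut the longest unchecked stretch of dosing from 25–30 days to 11–16 days. It would give the withdrawal provision in Section 4.5.1 a chance to act with 16 to 23 days of dosing remaining when a drug is found at a call.

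This rests on calls at Days 7 and 14, dosing from Day 0 to Day 30, and reading the diary as a study-drug record. The size is a delay in detection. It cannot be turned into a risk, because the documents give no frequency of new prescriptions and no rate of resulting harm. Confidence is medium, mainly because instructions in the consent form cannot be checked.

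**What to change.** 1. Mark Medications in the phone-call column of Table 1.
2. Extend Section 5.3 so that the review takes place at all study visits and scheduled calls.
3. Add to Section 5.3 that a newly started drug that may add bleeding risk and was barred at RA entry prompts the investigator to review whether ticagrelor should continue, under Section 4.5.1. These are antiplatelet therapy, chronic oral anticoagulation and, by inference from Section 4.2, a strong CYP 3A inhibitor. A new inducer can simply be recorded in answer to the same question.

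Stopping ticagrelor need not lose the Day 30 data: Section 4.5.2 encourages subjects taken off study drug for any reason other than an SAE to stay in the study and complete their visits.

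The cost is 50 to about 100 short questions, a CRF line and a minor amendment, which Section 11 requires to go to the IRB. No new contact is needed. The change shortens the gap without closing it: under the assumed call days, 11 to 16 dosing days after the Week 2 call still have no direct check.

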5.4 Receiving, Storage, Dispensing and Return

5.4.1 Storage and dispensing of Study drug

The following will be supplied by the Sponsor:

- 90 mg Ticagrelor tablets

Records will be maintained indicating the receipt and dispensation of all medication supplies.

CONFIDENTIAL

The Study drug will be stored between 15° to 30° C. The study drug will be labeled according to local regulatory requirements.

5.4.2 Return or Destruction of Study Drug

At the completion of the study, there will be a final reconciliation of drug shipped, drug consumed, and drug remaining. This reconciliation will be logged on the drug reconciliation form, signed and dated. Any discrepancies noted will be investigated, resolved, and documented prior to return or destruction of unused study drug. Drug destroyed on site will be documented in the study files.

6 Study Procedures

Study participation includes a 30-day treatment period. Screening and baseline visits may be done on the same day if the subject is able to give fasting blood and does not meet any exclusion criteria.

Table 1: Schedule of Assessments.

	Screening	Baseline	1 and 2 Week Phone call	Day 30
Visit #	1	1 or 2		2 or 3
Day#	- 30 - 3	0		30 ± 5
Informed consent	X			
Medical history	X	X		
Medications	X	X		X
Vital signs/physical exam		X		X
DAS28/CDAI/RAPID3/MDHAQ	X	X		X
ACR responses		X		X
Blood (fasting) collection		X		X
Urine and/or serum pregnancy test for WOCBP only	X	X		
Platelet Activity		X		X
Brachial Artery Reactivity Testing (fasting)		X		X
Dispense study drug		X		
Adverse events	X	X	X	X
Medication compliance/diary			X	X

6.1 Screening (Visit 1, Days -30 to -3)

- Patients will sign a written informed consent form prior to undergoing any study-specific activities;
- Patients will be assessed for inclusion/exclusion criteria;
- Demographics, medical history, review of medications will be performed;

CONFIDENTIAL

This material is the property of the NYU School of Medicine and Langone Medical Center. Do not disclose or use except as authorized in writing by the study sponsor

- DAS28, CDAI, RAPID3 and MDHAQ will be performed and records;
- Adverse events will be collected.

6.2 Baseline (Visit 1 or 2, Day 0)

- Medical history and review of medications will be performed;
- Vitals will be recorded and the patient will have a physical exam;
- DAS28, CDAI, RAPID3 and MDHAQ will be performed and recorded;
- ACR responses will be measured by the physician using patient questionnaires and joint counts;
- Fasting blood will be collected;
- For each subject, no more than 75 cc of blood will be collected in red (no anticoagulant) top, Pax gene tube for genomics, lavender (EDTA anticoagulant) top, green (heparin) and blue (sodium citrate anticoagulant) top tubes. Approximately 40 cc of blood will be used for the different measurements of platelet function, inflammation, immune activation, and other markers of cardiovascular risk, and approximately 30 cc of blood will be used to purify cells, RNA and DNA and then stored in -80C/liquid nitrogen for genetic and functional profiling. The results of the genetic testing will not be shared with the subjects.
 - The drawing of a maximum of 75 cc of blood is justified by the need for the above referenced tests, measurements and purification. These tubes will be drawn at the time of the standard of care blood draws for routine patient care monitoring. This amount of blood is medically safe to draw. The physician will always ensure the safety of drawing this volume of blood.
- Fasting brachial artery reactivity testing including one time dose of 0.4 mg of nitroglycerin given sublingual. To minimize risk of hypotension, nitroglycerin will not be administered if resting systolic blood pressure is <100 mmHg;
- Study medication will be dispensed;
- Adverse events will be collected.

